Self-Report Assessments: Participants will be instructed to complete each of the below questionnaires via an electronic survey (using the REDCap platform). These questionnaires are to be completed while the participant is on their video call with research staff to ensure that the questionnaires are being completed on the day of the study visit and that research staff is available to answer any questions and confirm that all questions have been answered. In the event that the participant does not have access to a computer and it is not feasible to complete these assessments electronically, a packet of blank questionnaires will be given to the participant at the end of each in-person study visit, that they will then complete during the remote portion of the next in-person visit. The participant will then return these completed

assessments to research staff at their next in-person visit. The coordinating center should be notified if these self-report assessments cannot be completed electronically.

- 12) Marijuana Withdrawal Checklist.
- 13) Marijuana Craving Scale.
- 14) Fagerstrom Test of Nicotine Dependence (week 4, and week 8 visits only).
- 15) VAS Mood States (paper copy of questionnaire provided to participant to complete).
- 16) VAS Marijuana Ladder.
- 17) Evening Morning Sleep Questionnaire (paper copy of questionnaire provided to participant to complete).
- 18) Pittsburg Sleep Quality Index

Should there be any perceived safety concerns, the participant may be asked to come into the clinic during the week of the remote study visit. For example, if unscheduled clinical labs need to be obtained as a result of a previous abnormal value, the participant will be asked to come into the clinical to complete only the blood draw, and all other procedures will be completed remotely.

9.6.4 Adherence to Study Medication: Approximately every morning, within a time period predetermined by agreement, participants will be called on the cell phone and will be observed removing study medication from the packaging and swallowing the medication with water or juice. The research assistant will log visual confirmation of adherence. A brief time line follow back assessment of cannabis and other drug use will be conducted. The entire process takes less than 5 minutes to complete.

9.6.5 Contingency Management: Participants will be asked about their use of cannabis or cannabinoid products daily on the CAROMA call. A successful "quit" attempt is defined as 1) an intentional (not lack of availability), 2) reduction (by 50% or more) in 3) the # of occasions of cannabis use in a day, 4) lasting a day (24 hours) or more, 5) compared to the average daily # of occasions of cannabis use captured by the last week screening TLFB for cannabis. Participants who have a successful quit attempt before the week 2 study visit will be eligible to receive \$50.

9.7 Follow-Up Phase Study Visits (Week 9 – Week 12): Upon completion of the 8-week treatment phase, participants will complete weekly follow up visits for four weeks primarily for safety purposes given that the effects of the study medication may take up to two weeks to wash out.

9.7.1 Week 9 In-Person Study Visit: The week 9 visit will serve as the end of treatment visit. This is an in-person study visit. The following procedures will be completed at this visit:

Remote Portion of Visit: Safety Procedures:

- 1) Review of medical and psychiatric history, including a review of all prescription or nonprescription medications, dietary and herbal supplements the participant is taking.
- 2) Administer the Columbia Suicide Severity Rating Scale (C-SSRS).

Remote Portion of Visit: Cannabis and Other Drug Outcomes:

- 3) 7-Day Timeline Follow Back Approach for Nicotine/Tobacco.
- 4) 7-Day Timeline Follow Back Approach for Alcohol.
- 5) 7-Day Modified Timeline Follow Back Approach for Cannabis: to verify the information on the participant's marijuana use that has been previously captured during the daily CAROMA calls, including the assigned dollar value.

- 6) The participant's desire to quit will be captured.
- 7) PRISM

Self-Report Assessments for Remote Portion of Visit: Participants will be instructed to complete each of the below questionnaires via an electronic survey (using the REDCap platform). These questionnaires are to be completed while the participant is on their virtual call with research staff to ensure that the questionnaires are being completed on the day of the study visit and that research staff is available to answer any questions and confirm that all questions have been answered. In the event that the participant does not have access to a computer and it is not feasible to complete these assessments electronically, a packet of blank questionnaires will be given to the participant at the end of each in-person study visit, that they will then complete during the remote portion of the next in-person visit. The participant will then return these completed assessments to research staff at their next in-person visit. The coordinating center should be notified if these self-report assessments cannot be completed electronically.

- 8) Marijuana Problems Scale.
- 9) Marijuana Withdrawal Checklist.
- 10) Marijuana Craving Scale.
- 11) VAS Marijuana Ladder.
- 12) Pittsburg Sleep Quality Index
- 13) Quality of Life Enjoyment and Satisfaction Questionnaire Short Form

In-Person Safety Visit Procedures:

- 1) Complete physical and neurological examination (this counts for check in with licensed clinician).
- 2) Record vital signs (sitting blood pressure, heart rate and temperature).
- 3) Alcohol breath test may be done at the discretion of the investigator based on clinical suspicion.
- 4) Record height and weight.
- 5) Obtain blood (hematology, clinical chemistry, LFTs) and urine samples (urinalysis) for safety laboratory tests.
- 6) Obtain urine sample for on site drug testing via a urine toxicology quick dip cup and for quantitative urine toxicology.
- 7) Blood drawn for PF-04457845 assay and serum endocannabinoid levels.
- 8) Administer urine pregnancy test for WOCBP
- 9) Record standard 12-lead electrocardiogram (ECG).
- 10) Ask participant about any adverse events. May be initially assessed remotely if the remote portion of the study visit occurs prior to the in-person portion of the study visit.
- 11) Pill counts will be performed for all medication dispensed since the last in-person study visit (2 weeks of medication).

In-Person Miscellaneous Outcomes:

- 12) Download actigraphy data, charge actigraph, and return to participant.
- 13) CogState Battery.
- 14) VAS Mood States
- 15) Evening Morning Sleep Questionnaire

9.7.2 Week 10 – Week 12 Remote Study Visits: At the Week 10, Week 11, and Week 12 follow up visits, safety data will be collected on the participant remotely. The following procedures will be completed for each participant:

- A check-in visit will be completed with a licensed clinician (MD, RN, APRN, PA). Research staff will assist in the coordination of this visit by arranging a time on the day of the remote study visit for the licensed clinician and research participant to have a video call.
- Review of medical and psychiatric history, including a review of all prescription or nonprescription medications, dietary and herbal supplements the participant is taking. Research staff will review this information with the participant, and will relay the updated information to the licensed clinician prior to the remote MD check-in visit.
- 3) Urine pregnancy test for WOCBP. At the Week 9 in-person study visit, all WOCBP participants will be provided with urine pregnancy tests to be completed remotely during the Week 10, Week 11, and Week 12 virtual study visits. During the remote visit, participants will be asked complete the pregnancy test and then hold the test up to the screen, so that research staff can visually see the results of the test.
- 4) Ask participant about any adverse events.
- 5) Administer the Columbia Suicide Severity Rating Scale (C-SSRS).
- 6) 7-Day Timeline Follow Back data will be collected for cannabis, alcohol, and nicotine/tobacco.
- 7) Marijuana Problems Scale (Week 11 only). Participants will be instructed to complete this assessment via an electronic survey (using the REDCap platform). This self-report assessment will be completed while the participant is on their virtual call with research staff. In the event that the participant does not have access to a computer or it is not feasible to complete electronically, a paper assessment will be given to the participant at the Week 9 visit which will then be returned at the End of Study Visit.

9.7.3 End of Study In-Person Visit: At the end of week 12 (~day 85), a visit will be conducted that will mark the end of the study. This visit will be completed both in-person and remotely. It is preferable that the remote portion of these study visits are completed prior to the in-person portion of the visit, and that both are completed on the same day (+/- 1). The following procedures will be completed at this visit.

Remote Portion of Visit: Safety Procedures:

- 1) Review of medical and psychiatric history, including a review of all prescription or nonprescription medications, dietary and herbal supplements the participant is taking.
- 2) Administer the Columbia Suicide Severity Rating Scale (C-SSRS).

Remote Portion of Visit: Cannabis and Other Drug Outcomes:

- 3) 7-Day Timeline Follow Back Approach for Nicotine/Tobacco.
- 4) 7-Day Timeline Follow Back Approach for Alcohol.
- 5) 7-Day Modified Timeline Follow Back Approach for Cannabis: to verify the information on the participant's marijuana use that has been previously captured during the daily CAROMA calls, including the assigned dollar value.
- 6) The participant's desire to quit will be captured.

Self-Report Assessments for Remote Portion of Visit: Participants will be instructed to complete each of the below questionnaires via an electronic survey (using the REDCap platform). These questionnaires are to be completed while the participant is on their virtual call with research staff to ensure that the questionnaires are being completed on the day of the study visit and that research staff is available to answer any questions and confirm that all questions have been answered. In the event that the participant does not have access to a computer and it is not feasible to complete these assessments electronically, a packet of blank questionnaires will be given to the participant at the end of each in-person study visit,

that they will then complete during the remote portion of the next in-person visit. The participant will then return these completed assessments to research staff at their next inperson visit. The coordinating center should be notified if these self-report assessments cannot be completed electronically.

- 7) Marijuana Problems Scale.
- 8) Marijuana Withdrawal Checklist.
- 9) Marijuana Craving Scale.
- 10) VAS Marijuana Ladder.
- 11) Pittsburg Sleep Quality Index

In-Person Safety Visit Procedures:

- 16) A check-in visit will be completed with a licensed clinician (MD, RN, APRN, PA).
- 17) Record vital signs (sitting blood pressure, heart rate and temperature).
- 18) Alcohol breath test may be done at the discretion of the investigator based on clinical suspicion.
- 19) Record height and weight.
- 20) Obtain blood (hematology, clinical chemistry, LFTs) and urine samples (urinalysis) for safety laboratory tests.
- 21) Obtain urine sample for on site drug testing via a urine toxicology quick dip cup and for quantitative urine toxicology.
- 22) Blood drawn for PF-04457845 assay and serum endocannabinoid levels.
- 23) Administer urine pregnancy test for WOCBP
- 24) Ask participant about any adverse events. May be initially assessed remotely if the remote portion of the study visit occurs prior to the in-person portion of the study visit.

In-Person Miscellaneous Outcomes:

- 25) Download actigraphy data.
- 26) VAS Mood States
- 27) Evening Morning Sleep Questionnaire

9.8 Participant Reimbursement: All participants will be compensated for their participation in various study procedures. Please refer to Table 12 for the full breakdown of participant payment. In addition, participants will receive escalating payments contingent on attending their appointments and completing study related procedures. Participants will be repeatedly told before the study and reminded once enrolled in the study that the contingency management payments are not linked to abstinence from cannabis. Participants will be compensated for the remote study visits at the next subsequent in-person visit.

STUDY VISITS	REGULAR	ADHERENCE	TOTAL	
310D1 VI3113	PAYMENTS	PAYMENTS	IUTAL	
Screening	\$50	\$0	\$50	
Week 1	\$40	\$0	\$40	
Successful quit attempt	\$50	\$0	\$50	
Week 2	\$20	\$20	\$40	
Week 3	\$25	\$25	\$50	
Week 4	\$30	\$35	\$65	
Week 5	\$35	\$50	\$85	
Week 6	\$40	\$70	\$110	

Table 12: Participant Payme	ents
-----------------------------	------

APPROVED BY THE YALE UNIVERSITY IRB 5/1/2022

Week 7	\$45	\$95	\$140
Week 8	\$50	\$125	\$175
Week 9	\$55	\$160	\$215
Week 10	\$60	\$0	\$60
Week 11	\$65	\$0	\$65
Week 12	\$70	\$0	\$70
End of study	\$75	\$0	\$75
Payment for returning phone	\$50	\$0	\$50
Total	\$760	\$580	\$1,340

9.9 *Early Termination Study Visit:* If a participant decides to withdraw from the study after randomization or is terminated by the site principal investigator for any reason after randomization, an early termination study visit will be conducted to close out the participant from the study. At this visit the participant will be instructed to return all unused study medication. The Week 9 procedures will be attempted at an early termination visit, which will be conducted per Section 9.7.1, both in person and remotely.

10.0 ASSESSMENTS:

Every effort should be made to ensure that protocol-required tests and procedures are completed as described. When a protocol-required test cannot be performed, study staff will be instructed to document the reason for the missed test and any corrective and preventative actions which s/he has taken to ensure that required processes are adhered to as soon as possible. Any protocol deviations should be documented in the study log.

10.1 Blood: Total blood sampling volume for the individual participants is approximately 420 mL over approximately 14 weeks of the study. The actual times of blood sampling may change. Additional blood samples may be taken for safety assessments at times specified by the Coordinating Center, provided the total volume taken during the study does not exceed 450 mL (safety, PF-04457845 levels, endocannabinoid levels).

10.2 Safety:

10.2.1 Laboratory Tests: The following safety laboratory tests will be performed at the following study visits: Screening, Week 1, Week, 5, Week 7, Week 9, and End of Study Visit (end of Week 12). They are conducted periodically throughout the duration of the study to monitor electrolyte and liver/kidney function. Additional laboratory results may be generated on the samples (without additional blood volume drawn) as a result of the method of analysis, the type of analyzers used, or as derived or calculated values; if such results are available, they may also be reported. Unscheduled clinical labs may be obtained at any time during the study to assess any perceived safety concerns.

Hematology: Hemoglobin, Hematocrit, RBC Count, MCV, MCHC, RDW, MCH, MPV, Platelet Count, WBC Count, Total Neutrophils (Abs), Eosinophils (Abs), Monocytes (Abs), Basophils (Abs), Lymphocytes (Abs); Collected using one 10cc Lavender-top Tube (tube contains EDTA as an anticoagulant).

Chemistry: BUN and Creatinine, BUN/Creatinine Ratio, Glucose, Calcium, Sodium, Potassium, Chloride, Total CO2, AST, ALT, Total Bilirubin, Direct Bilirubin, Alkaline Phosphatase, Urine acid, Albumin, Total protein, HDL, LDL, Cholesterol; Collected using one 10 cc Tiger-top Tube (tube does not contain an anticoagulant but does contain a clot activator and serum separator gel).

Urinalysis: Color, Appearance, Specific Gravity, pH, Glucose, Protein, Blood, Ketones, Nitrites, Leukocyte esterase, Bilirubin, Urobilinogen, Bacteria, Casts, Crystals, Yeast, Amorphous Sediment, Epithelial Cells, WBC, RBC; Collected using one 10cc urinalysis preservative tube (tube includes a preservative of chlorhexidine, ethylparaben, and sodium propionate).

On-Site Urine Drug Testing: At every study visit, participants will be tested using a urine drug quick dip. A 12-panel all-in-one drug test cup with a built-in temperature strip (CLIA waived) should be used for these quick dip urine drug tests. The minimum requirement for drug testing includes:

- 1. Amphetamines (Detection Period: 1-2 days; Cutoff Level: 1000 ng/mL)
- 2. Barbiturates (Detection Period: 1-4 days; Cutoff Level: 200 ng/mL)
- 3. Buprenorphine (Detection Period: 1-3 days; Cutoff Level: 10 ng/mL)
- 4. Benzodiazepines (Detection Period: 1-2 days; Cutoff Level: 200 ng/mL)
- 5. Cocaine (Detection Period: 2-4 days; Cutoff Level: 300 ng/mL)
- 6. THC-COOH (Detection Period: up to 5+ days; Cutoff Level: 50 ng/mL)
- 7. Methamphetamines (Detection Period: 2-4 days; Cutoff Level: 500 ng/mL)
- 8. Methylenedioxymethamphetamine (Detection Period: 2-4 days; Cutoff Level: 1000 ng/mL)
- 9. Methadone (Detection Period: 1-3 days; Cutoff Level: 300 ng/mL)
- 10. Opiates (Detection Period: 2-3 days; Cutoff Level: 300 ng/mL)
- 11. Oxycodone (Detection Period: 1-3 days; Cutoff Level: 100 ng/mL)
- 12. Phencyclidine (Detection Period: 7-14 days; Cutoff Level: 25 ng/mL)

If during the in-person visits a sample tests positive for any drug (other than THC) on site, a sample will be sent to the laboratory for confirmation.

Participants may undergo random urine drug testing at the discretion of the investigator. Spot urine drug testing conducted prior to dosing must be positive for cannabinoids for participants to receive study medication.

On Site Urine and Serum Pregnancy Test: Urine HCG testing should first be performed using a urine pregnancy spot kit. If the result yields a positive result, then a serum HCG test will be sent out for confirmation. If the result yields a positive result during one of the remote study visits the participant will be asked to come in to the clinic to provide a blood sample and study medication will be suspended. For the serum HCG test, a blood serum sample will be collected using one 10 cc Tiger-top Tube (tube does not contain an anticoagulant but does contain a clot activator and serum separator gel).

Quantitative Urine Cannabinoids Toxicology: Urine samples will be collected at each of the inperson visits as specified in the Schedule of Procedures (**1.5 Schedule of Procedures:**

Table 2). At each in-person visit, a urine sample will be obtained from the participant, pipetted into one 1.5 mL cryovial tube (urine sample should be filled up to the top line of the tube), and will be stored in a -80 degree Celsius freezer until the sample is ready for shipment. Samples will be shipped in batches, on dry ice, directly to the lab of [name] at the Nathan Kline Institute: [name]. The Coordinating Center will instruct each individual site on when to ship these samples to [name], at intervals of approximately 6 months. Levels of THC-COOH the principal inactive metabolite of cannabis will be assayed by the lab of [name] at the Nathan Kline Institute in 6 month batches using a GCMS method (205). Assays have intra- and inter-assay RSD% of 10% at 1 ng/ml with 0.5 ng/ml as the lower limit of detection. Creatinine corrected THC-COOH levels will be reported.

10.2.2 Vital Signs: Blood pressure, pulse rate, oral temperature, height and body weight will be measured periodically and recorded, as specified in **1.5** Schedule of Procedures:

Table 2, the Study Procedures Table. Sitting blood pressure will be measured with the participant's arm supported at the level of the heart, and recorded to the nearest mm Hg after at least 5 minutes of rest. The same arm (preferably the dominant arm) will be used throughout the study.

The same size blood pressure cuff, which has been properly sized and calibrated, will be used to measure blood pressure each time. The use of automated devices for measuring BP

and pulse rate are acceptable, although, when done manually, pulse rate will be measured in the brachial/radial artery for at least 30 seconds. When the timing of these measurements coincides with a blood collection, blood pressure and pulse rate should be obtained prior to the nominal time of the blood collection.

A participant should have weight and height measured while wearing indoor clothing and with shoes off. The standard for collecting height is inches without decimal places and for weight it is pounds with one decimal place. BMI will be calculated for each participant through the Table listed in Appendix I.

10.2.3 Physical Examinations: Completed physical and neurological examinations will be conducted at screening and at the end of the treatment phase or early termination visit. Physical examinations will be conducted by a physician, trained physician assistant, or nurse practitioner, as designated by the site principal investigator.

10.2.4 Electrocardiogram (ECG): ECGs should be collected after the participant has rested quietly for at least 10 minutes in a supine position. When the timing of these measurements coincides with a blood collection, the ECG should be obtained prior to the nominal time of the blood collection, blood pressure, and pulse rate.

A standard 12-lead ECG will be recorded. A qualified individual appointed by the site investigator will make comparisons to baseline measurements. If interpreted as abnormal, the local investigator will assess the findings as either abnormal clinically significant, or abnormal not clinically significant. The interpretation of the ECG will be recorded in the source documents. ECG traces recorded on thermal paper will be photocopied to avoid degradation of the trace over time.

10.3 Pharmacokinetics:

10.3.1 PF-04457845 Levels: Blood will be sampled for PF-04457845 levels as specified in the Schedule of Procedures (1.5 Schedule of Procedures: Table 2). Given that adherence will be confirmed visually, the PF-04457845 levels will be assayed in only a random sampling of approximately 1/3 of participants from each site to confirm adherence, as specified by the Coordinating Center. Assays will be conducted by laboratory of [name] at Northeastern University using a proprietary assay with existing permission from SpringWorks and Jazz Pharmaceuticals. The serum sample to be analyzed for PF-04457845 levels should be collected in one 4 cc lavender top tube (tube containing K2-EDTA). Blood samples should be collected as close to approximately 1 hour after the participant has taken their daily dose of study medication (PF-04457845/placebo). The time at which the blood sample has been drawn at should be documented, along with the time that the study medication was taken that day. The sample should then be centrifuged at approximately 1700g for about 10 minutes at 4 degrees Celsius, pipetted into appropriately labeled 1.5 mL screw capped polypropylene tubes (1 mL of serum sample per tube; 2 polypropylene tubes), and then stored in a -80 degree Celsius freezer within 1 hour of collection. Samples will be stored on site until they are to be sent directly to WuXi by each site, at the end of the study.

Shipment of Pharmacokinetic Samples: Each site will store blood samples to be assayed for PF-04457845 levels on site in a -80 degree Celsius freezer. Samples will be stored on site, and will be shipped on dry ice directly to the lab of [name] at Northeastern University, in batches of at least 50 samples. The Coordinating Center will instruct each individual site on which random sampling of participants should be shipped.

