Weeks (days)		(-14)	(-7)	1 (Quit Attempt after day 2)	2	3	4	5	6	7	8	9	10	11	12	End		
Vis	sit	1	2	3	5	6	7	8	9	10	11	12	13	14	15	16		
	In Person		Х	Х		Х		Х		Х		Х				Х		
Visit Type	Remote	Х			Х		Х		X		Х		X	Х	Х			
Drug	PF- 04457845			x	x	x	x	x	x	x	x							
Condition	Placebo			х	х	х	х	х	х	х	х							

1.5 Schedule of Procedures:

Table 2: Schedule of Procedures

*Weekly visits after randomization occur every 7 days \pm 3 days

	Visit* (R=Remote ; IP= In-Person)		In-Person Screening		Week 2 R	Week 3 IP / R	Week 4 R	Week 5 IP / R	Week 6 R	Week 7 IP / R	Week 8 R	Week 9 IP / R	Week 10 R	Week 11 R	Week 12 R	End of Study IP / R
	Study Phase	Pre-Rand					Treatme	nt Phase)				F	ollow Up	Phase	
	Day*	-14	-7	1	8	15	22	29	36	43	50	57	64	71	78	85
Informed Cor	nsent & Supplement to Consent Questionnaire	x														
Psychiatric	SCID	x														
Evaluation	Demographic data	х														
	Chemistry, hematology, LFTs		X (IP)	X (IP)				X (IP)		X (IP)		X (IP)				X (IP)
-	DNA Sample collection		X (IP)													
	UTOX (spot - on site)	x	X (IP)	X (IP)	x	X (IP)	х	X (IP)	x	X (IP)	х	X (IP)				X (IP)
	Urine Pregnancy Test for WOCBP	х	X (IP)	X (IP)	x	X (IP)	x	X (IP)	x	X (IP)	х	X (IP)	х	х	x	X (IP)
	Urinalysis		X (IP)	X (IP)				X (IP)		X (IP)		X (IP)				X (IP)
Safety	Physical Examination		X (IP)									x				
-	EKG		X (IP)	X (IP)								x				
	Concomitant medication check	x		х	x	x	х	x	x	х	х	x	х	х	x	x
	Columbia Suicide Severity Rating Scale	x		х	x	x	х	x	x	х	х	x	х	х	x	x
	Adverse Events (SAFTEE)	x	X (IP)	X (IP)	x	X (IP)	x	X (IP)	x	X (IP)	x	X (IP)	х	х	х	X (IP)
	Licensed Clinician (MD, RN, APRN, PA) check-in	x	X (IP)	X (IP)	X (IP)	x	x	x	x	x	х	x	х	х	x	x
	Lifetime Cannabis Use (SALCU)	x	. ,	. ,												
	Urine Creatinine: THC-COOH Quantification		X (IP)	X (IP)		X (IP)		X (IP)		X (IP)		X (IP)				X (IP)
MJ Use	TLFB-cannabis (30 day, 7 day)	-30	-7 (IP)	-7	-7	-7	-7	-7	-7	-7	-7	-7	-7	-7	-7	-7
Quantification	\$ spent on MJ	-30	-7 (IP)	-7	-7	-7	-7	-7	-7	-7	-7	-7	-7	-7	-7	-7
	CAROMA (daily TLFB)			х	x	x	x	x	x	x	x					
Willingne	ess to Attempt Quitting (signed statement)	x	X (IP)	X (IP)												
	Contingency management for self-reported quit attempt		, (ii)	\$50												
Junig	Motivational Interviewing	x	X (IP)	+												
	Randomization of Participant			X (IP)												
	Desire to Quit	x	X (IP)	X (IP)	x	X (IP)	x	X (IP)	x	X (IP)	x	X (IP)				X (IP)
	Marijuana Problems Scale	x	X (IP)	X (11)	~		~	, ()	~		~	x (ii)		x		x

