- 8) Ask participant about any adverse events. May be initially assessed remotely if the remote portion of the study visit occurs prior to the in-person portion of the study visit.
- 9) Pill counts will be performed for all medication dispensed since the last in-person study visit (2 weeks of medication).
- 10) Medication will be dispensed for the following two weeks (so the participant will have enough study medication until their next in-person study visit).
- 11) A check-in visit will be completed with a licensed clinician (MD, RN, APRN, PA). The Week 1 and Week 3 check-in visit should be completed in-person. Of note, the MD check-in visits must be completed last so that the MD has all of the necessary information to evaluate the participant.

In-Person Miscellaneous Outcomes:

- 12) Download actigraphy data, charge actigraph, and return to participant.
- 13) CogState Battery (Week 1 only).
- 14) VAS Mood States
- 15) Evening Morning Sleep Questionnaire

Of note, prior to the participant leaving each in-person visit research staff will provide them with a quick dip urine toxicology cup to complete during the following week's remote visit and a pregnancy test for WOCBP to complete during the next week's remote visit. They will also be provided with a hard copy of the VAS Mood States and Evening Morning Sleep Questionnaires. In the event that the participant does not have access to a computer, they will also be provided with a packet of the blank self-report assessments to be completed during the following week's remote visit.

9.6.3 Remote Treatment Phase Study Visits (Week 2, Week, 4, Week 6, and Week 8)

Procedures: The Week 2, Week 4, Week 6, and Week 8 study visits will be conducted remotely, utilizing the same method as the daily CAROMA calls (video call using the clinic provided cell phone). Prior to beginning each remote visit, research staff will confirm that study participant is

in an area where they have privacy and will be undisturbed. During each remote study visit, the following procedures will be completed (**1.5** Schedule of Procedures:

Safety:

- Review of medical and psychiatric history, including a review of all prescription or nonprescription medications, dietary and herbal supplements the participant is taking. Research staff will review this information with the participant, and will relay the updated information to the licensed clinician prior to the remote MD check-in visit.

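### Sections 9.6.2 and 9.6.3 disagree on when paper questionnaires for the remote weeks are completed; followed literally, 9.6.3 puts the Week 2, 4, 6 and 8 forms about 7 days late

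*Combined protocol and SAP*

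**What the plan says.** Section 9.6.3 covers the remote visits at Weeks 2, 4, 6 and 8. It opens "During each remote study visit, the following procedures will be completed", and its list includes the Marijuana Withdrawal Checklist, Marijuana Craving Scale, Marijuana Ladder and PSQI, with the FTND at Weeks 4 and 8. Electronic surveys are the default. They are done on the video call "to ensure that the questionnaires are being completed on the day of the study visit".

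The paper fallback applies when the participant "does not have access to a computer and it is not feasible to complete these assessments electronically". The packet is handed out at the end of an in-person visit and is one "that they will then complete during the remote portion of the next in-person visit". Completed forms are returned at the next in-person visit, and the coordinating center is to be notified.

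The closing paragraph of 9.6.2 covers what participants take home from an in-person visit. For those without a computer, "they will also be provided with a packet of the blank self-report assessments to be completed during the following week's remote visit".

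Table 2 marks the withdrawal and craving scales at every week from Week 2 to Week 9 and at End of Study. Its footnote sets the spacing: "Weekly visits after randomization occur every 7 days", with a window of 3 days either way.

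**The concern.** The two instructions cannot both govern the same forms. One places a remote week's questionnaires in that week; the other places them at the next in-person visit, when most of the same scales are due again. With four sites, the conflict could be settled differently from site to site, and the documents give no rule for choosing.

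What is at stake is the timing of repeated exploratory measures. A site using the 9.6.3 clause would hold two same-day copies of the weekly scales, one of them meant for the previous week. Week 2 matters most because it is the first scheduled withdrawal and craving assessment after the quit date. Under 10.11 the craving form asks how the respondent feels while filling it in, so one completed at Week 3 is a Week 3 score whatever week it is filed under. Section 10.10 states no recall period for the Withdrawal Checklist, so for that scale it is safer to say only that the score is displaced.

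**Working it through.** No stated figure in the plan depends on this point. The check compares the passages and applies date arithmetic to the nominal days in Table 2.

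**1. Where the fallback clause fits.** Essentially the same sentence appears in 9.6.2, 9.7.1 and 9.7.3. Those in-person visits have a remote portion, so the clause works there. Within 9.6.2 it can also coexist with the closing paragraph: one packet serves the remote portion of the next in-person visit, and another serves the remote week in between. In 9.6.3 that reconciliation fails. The section concerns only remote weeks, and the clause is its only instruction on when their paper packet is completed. It reads as text carried over.

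**2. Displacement if 9.6.3 is followed literally** (nominal days from Table 2):

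| Remote week (day) | Next in-person week (day) | Delay |
|---|---|---|
| 2 (8) | 3 (15) | 15 − 8 = 7 days |
| 4 (22) | 5 (29) | 29 − 22 = 7 days |
| 6 (36) | 7 (43) | 43 − 36 = 7 days |
| 8 (50) | 9 (57) | 57 − 50 = 7 days |

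If the 3-day window is applied to each nominal day, the delay for each pair runs from 7 − 6 = 1 day to 7 + 6 = 13 days. Under the close of 9.6.2 the delay is 0.

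**3. Time since the quit date.** Section 9.6.1 puts the quit date on Day 3 to Day 7.

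- Week 2, nominal: 8 − 7 = 1 to 8 − 3 = 5 days after quitting.
- Week 3, nominal: 15 − 7 = 8 to 15 − 3 = 12 days after quitting.
- Week 2 with its window (Day 5 to 11): 5 − 7 = −2 to 11 − 3 = 8 days.
- Week 3 with its window (Day 12 to 18): 12 − 7 = 5 to 18 − 3 = 15 days.

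Section 2.4 describes most withdrawal symptoms as peaking 2 to 3 days into abstinence and typically resolving in 1 to 2 weeks, with some studies suggesting persistence beyond 4 weeks. On nominal days, Week 2 is the scheduled assessment nearest that peak; Week 3 falls later.

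**4. Share of scores.** Weeks 2 to 9 give eight withdrawal and eight craving scores. Weeks 2, 4, 6 and 8 are displaced, so 4 of 8. Counting End of Study as well, it is 4 of 9 post-baseline scores.

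**5. Same-day duplication.** The Withdrawal Checklist, Craving Scale, Ladder and PSQI are all listed again for Weeks 3, 5 and 7 (9.6.2) and Week 9 (9.7.1). The FTND is not, so its Week 4 and Week 8 forms would be late but not duplicated.

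**The case against.** The strongest reply is that the intended timing is plain. The take-home instruction in 9.6.2, the opening of 9.6.3, its aim of same-day completion, and Table 2 all point to completion in the remote week. A careful site would probably do this correctly. That stands, and it is why the point is minor. It does not remove the conflict, because the contrary clause sits in the section that a coordinator would consult for a remote visit.

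The affected group may also be small. The 9.6.3 fallback needs both no computer and no feasible electronic route, every participant receives a study smartphone for remote procedures (9.5.5), and the coordinating center is told of exceptions. This stands too. The documents give no count, so none is offered here.

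The link to the withdrawal peak is loose. Visit windows are wide, Section 2.4 allows longer courses, and 9.6.5 counts a reduction of 50% or more lasting a day as a successful quit, whereas the Section 2.4 time course is for abstinence. The comparison in days is therefore descriptive only.

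A reader might infer that the Week 2 withdrawal and craving scores are never taken. The documents do not support that. No passage tells sites to skip Week 2, and several schedule it. Even the literal 9.6.3 clause has the forms completed, only later. Nor do the documents say under which week a late form would be entered.

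**Conclusion.** The inconsistency is real and minor. For participants on the paper route, 9.6.3 and the close of 9.6.2 give different completion times. The stated size rests on three conditions: a site follows the 9.6.3 clause literally, visits fall on nominal days, and the participant has no feasible electronic route.

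The consequences reach exploratory endpoints only. Craving and withdrawal are in the exploratory list of 4.2.3 (which names the withdrawal instrument as the Cannabis Withdrawal Scale; the scheduled checklist is taken here as that measure), as are the sleep questionnaires. The Ladder and FTND are not named as endpoints in 4.2. VAS Mood States, itself an exploratory withdrawal measure, goes to everyone on paper for remote weeks and does not depend on computer access. The primary endpoint, the secondary endpoints in 4.2.2 and the sample size are unaffected.

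**What to change.** In 9.6.3, replace the clause on when the packet is completed with: that they will then complete, and date, during that week's remote visit while on the video call. Keep the return of the forms at the next in-person visit. This brings 9.6.3 into line with the close of 9.6.2 and with Table 2. The wording in 9.6.2, 9.7.1 and 9.7.3 can stay.

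The cost is one clause and a note to the four sites. If any participant has already used the paper route, the notifications to the coordinating center should identify them, and any completion dates on their forms can be checked against the visit dates. A craving score collected in the wrong week cannot be recovered afterwards.
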